2.2 Secondary Objectives

2.2.1 To prospectively characterize MCD presentation in Malawi.

2.2.2 To determine overall survival rate.

2.2.3 To determine event-free survival rate.

2.2.4 To describe the efficacy of the risk-adjusted treatment protocol as determined by clinical response rates at end of treatment and 12 weeks after start of treatment.

2.2.5 To describe radiologic response rates at end of treatment and 12 weeks after start of treatment.

2.2.6 To further characterize the safety by describing the frequency of all AEs with risk-adjusted treatment-protocol for MCD in Malawi.

2.2.7 To describe the rate of Kaposi sarcoma exacerbation, as defined by symptomatic or clinical (dermatologic or visceral organ) exacerbation of disease in patients receiving the risk-adjusted treatment protocol.

2.2.8 To describe the quality of life of patients with MCD before, during and after treatment with a rituximab-based, risk-adjusted treatment protocol, as assessed by the MCD symptom score and PROs.⁴²

2.2.9 To describe the trends in hemoglobin, platelet count, C-reactive protein (CRP), and IL-6 before, during, and after a risk-adjusted, rituximab-based treatment protocol

for MCD in Malawi and describe the utility of these markers as a predictor of relapse.

2.2.10 To evaluate for predictors of relapse or refractory disease with a risk-adjusted, rituximab-based treatment protocol.

2.2.11 To evaluate changes in Kaposi sarcoma viral load as a result of treatment.

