3.2 Secondary Endpoints

3.2.1 At study entry, basic demographics and baseline laboratory values will be summarized using descriptive statistics (i.e., means, medians, and variability measures for continuous variable; rates and proportions for binary variables). Screening assessments to be completed within 21 days prior to study enrollment.

3.2.2 Overall survival will be assessed at 12 weeks, one year, and two years from the start of treatment.

3.2.3 Event-free survival will be defined as the rate of refractory disease, relapse (same definition of active disease as in the inclusion criteria in section 4.1), non-Hodgkin lymphoma development or death and will be assessed at 12 weeks, one year, and two years from the start of treatment.

3.2.4 Clinical response rate at end of treatment and 12 weeks from treatment initiation (clinical response defined as resolution of presenting signs/symptoms that defined

the Multicentric Castleman disease (MCD) attack) without relapse at 12 weeks. MCD attack/flare is defined in Section 4.1.1.

3.2.5 Radiologic response rate is the percentage of patients without relapse at end of treatment and 12 weeks from treatment initiation. Chest radiography and abdominal sonography will be used for staging. Per Revised response criteria for gross lymphadenopathy, response will be evaluated via complete survey of lymph nodes with measurements and physical assessment of other palpable masses with measurements.

Response criteria for lymph node response will be as follows: Complete response (CR)- disappearance of all evident disease; Partial response (PR)-at least 50% decrease in target lesions with no increase in non-target lesions, Stable disease (SD)- Neither sufficient shrinkage to qualify for PR nor sufficient increase to qualify for progressive disease (PD); PD- appearance of a new lesion or at least a 50% increase in lesion size.

3.2.6 Additional safety assessment will be graded by CTCAE v 5.0 through 12 weeks from the start of therapy.

3.2.7 Kaposi sarcoma exacerbation will be defined as new symptoms attributed to KS or clinically evident exacerbation of dermatologic or visceral disease. All disease flares will be biopsy confirmed whenever possible.

3.2.8 Quality of life will be assessed by the MCD symptom score, a patient-reported outcomes questionnaire, and PROMIS Global 10, at baseline (week 1), 15 days (week 3), end of treatment (week 5), 12 weeks, 6 months, and 24 months after treatment, and at the time of any relapse.

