4.2 Exclusion Criteria

All subjects meeting any of the following exclusion criteria at time of enrollment will be excluded from study participation.

4.2.1 Symptomatic, extensive-stage KS (T1 by the ACTG staging system; T1 includes ulceration or edema from KS, raised or non-hard palate oral lesions, or any visceral

involvement) requiring urgent treatment, to avoid potential rituximab-induced KS worsening.

- 4.2.2** Previous rituximab use for MCD.
- 4.2.3** Second active malignancy requiring systemic therapy.
- 4.2.4** If HIV negative and a) hepatitis B virus surface antigen positive or unless on tenofovir or lamivudine. All HIV-infected patients must be on tenofovir or lamivudine as part of the inclusion criteria.
- 4.2.5** Active infection requiring systemic therapy.
- 4.2.6** Treatment with any investigational drug within 28 days prior to registration.
- 4.2.7** More than 7 days of corticosteroids immediately prior to enrollment. If subject is taking corticosteroids for more than 7 days, they require a 7 day washout period before enrollment.
- 4.2.8** Bilirubin >3 mg/dL.
- 4.2.9** Creatinine clearance <30 ml/min by Cockcroft-Gault formula.
- 4.2.10** ECOG performance status >3.
- 4.2.11** Pregnant or breastfeeding (NOTE: breast milk cannot be stored for future use while the mother is being treated on study).

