10.0 STATISTICAL CONSIDERATIONS

10.1 Study Design/Study Endpoints

This is a single arm, prospective, phase II clinical trial for safety and efficacy of risk-stratified treatment with rituximab +/- chemotherapy for MCD. Eligible patients will be enrolled and treated according to the study schema. High-risk patients (defined as patients with ECOG performance status >2 or hemoglobin <8 g/dL during screening or enrollment)^{9,10,13-16} will receive four weekly doses of rituximab (375 mg/m²) and etoposide

(100 mg/m²) as in Bower, et al.⁹ Note that patients with low hemoglobin within the last month that receive a blood transfusion as treatment will be considered high risk if their pre-transfusion hemoglobin was <8 g/dL. Low-risk patients will receive the same dose of rituximab alone. The planned sample size is 27 patients and the primary outcome is safety. Secondary outcomes include one- and two-year EFS (relapse, development of NHL, or death), OS, and KS exacerbation rates. We will also collect clinical, laboratory, virologic data, and stored samples at baseline and end-of-treatment to both describe the presentation of MCD in our population and to evaluate risk factors for death or relapse. Finally, we will conduct comprehensive microcosting analysis and a Markov model cost-effectiveness analysis.

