10.5 Secondary Objectives

10.5.1 To better characterize MCD presentation in Malawi.

Basic demographics and baseline laboratory values will be summarized using descriptive statistics (i.e., means, medians, and variability measures for continuous variable; rates and proportions for binary variables).

10.5.2 To describe the efficacy of the risk-adjusted approach as determined by clinical and radiologic response rates, 90-day, one-year, and two-year EFS and OS.

An event for EFS is either relapse (defined as “MCD attack” in the Inclusion Criteria (section 4.1)), refractory disease, lost-to-follow-up (LTFU), or death. We will consider patients LTFU if they cannot be contacted by phone for three months. Given the high mortality associated with MCD and previously published literature supporting a strong association between LTFU and mortality in SSA, we will consider LTFU as a failure event for both EFS and OS.⁴³ Relapse for purposes of this study will be defined as recurrence of an “MCD attack” (Inclusion Criteria; section 4.1) requiring re-initiation of treatment, with a strong preference for biopsy-proven recurrence whenever possible. We will conduct survival analysis using Kaplan-Meier methods. Radiologic response will be assessed in parallel with clinical response with response criteria defined in section 7.1.7. We will assess the prognostic value of radiologic response for EFS and OS in Cox proportional hazards model.^{10,15,16}

10.5.3 To describe the safety, as determined by the rate of all AEs during a risk-adjusted approach to treatment of MCD in Malawi.

All AEs will be described up to 30 days after final dose of MCD-directed treatment.

10.5.4 To describe the rate of KS exacerbation, as defined by symptomatic or clinical (dermatologic or visceral organ) exacerbation of disease.

The rate of KS exacerbation will be reported as the number of KS cases requiring KS-specific treatment divided by the number of patients with pre-existing KS (as defined by personal history of KS, baseline presence of KS, or KS in lymph node biopsy). This will be estimated along with a 95% confidence interval for the proportion.

10.5.5 To describe the quality of life of patients with MCD before, during and after treatment with a rituximab-based, risk-adjusted treatment approach, as assessed by the MCD symptom score⁴² and PROPr instrument.⁴⁴

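### The KS exacerbation rate in section 10.5.4 counts only KS needing KS-specific treatment, while the endpoint in 2.2.7 and 3.2.7 is symptomatic or clinically evident worsening, treated or not

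*Combined protocol and SAP*

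**What the plan says.** Three places define the event, and none mentions treatment:

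- Objective 2.2.7: "To describe the rate of Kaposi sarcoma exacerbation, as defined by symptomatic or clinical (dermatologic or visceral organ) exacerbation of disease".
- Endpoint 3.2.7: "Kaposi sarcoma exacerbation will be defined as new symptoms attributed to KS or clinically evident exacerbation of dermatologic or visceral disease".
- The heading of 10.5.4: "To describe the rate of KS exacerbation, as defined by symptomatic or clinical (dermatologic or visceral organ) exacerbation of disease".

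The analysis text under that heading then sets the estimator. The numerator is in "The rate of KS exacerbation will be reported as the number of KS cases requiring KS-specific treatment". The denominator is in "divided by the number of patients with pre-existing KS (as defined by personal history of KS, baseline presence of KS", with KS found in the lymph node biopsy as a third route in. On precision: "This will be estimated along with a 95% confidence interval for the proportion". No test, alpha, power or decision rule is attached.

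Section 10.1 names the outcome ("OS, and KS exacerbation rates") without a formula, and section 5.1 does the same. Neither 3.2.7 nor 10.5.4 states a follow-up window for the rate.

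**The concern.** The endpoint and its estimator describe different events. A patient whose skin lesions visibly worsen, or who develops new KS symptoms, has an exacerbation under 3.2.7. If nobody judges that KS-specific treatment is needed, that patient does not enter the 10.5.4 numerator.

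KS flare is a risk that the protocol itself attaches to rituximab. Exclusion 4.2.1 removes symptomatic extensive KS "requiring urgent treatment, to avoid potential rituximab-induced KS worsening", and section 1.3 cites an exacerbation risk of 36-75% in patients with pre-existing KS. A treatment-based rate set beside such figures could look reassuring only because it counts a narrower event.

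**Working it through.** **Is there a planned figure to reproduce?** No. The documents give no expected rate, event count or sample size for this endpoint. The check is a comparison of definitions, followed by a bound on what each reclassified patient does to the rate.

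**Definitions compared**

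| Patient with pre-existing KS | Exacerbation under 3.2.7 | Counted in 10.5.4 |
|---|---|---|
| Worsens, KS-specific treatment required | Yes | Yes |
| Worsens, treatment not required | Yes | No |
| Does not worsen, no treatment required | No | No |

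The second row is the gap. The two rates agree only if that row is empty.

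**Is that row plausible?** Exclusion 4.2.1 keeps out symptomatic T1 KS needing urgent treatment. The denominator admits patients with only a history of KS, or KS seen only in a node biopsy. Some pre-existing KS therefore starts mild, where visible worsening need not lead to treatment. The treatment criterion is also loosely specified. KS-specific treatment is not defined, high-risk patients already receive etoposide (which section 1.4 describes as a KS treatment), and section 5.5 prohibits systemic therapy for other active malignancies. Whether a flare counts may then depend on protocol rules as well as on the KS.

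**Does another section supply the 3.2.7 rate?**

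- Sections 5.1 and 10.1 only name the outcome.
- Section 10.4.1 estimates rates for individual adverse events and 10.5.3 describes all adverse events to 30 days after the final dose. Neither gives a rate among patients with pre-existing KS.
- Sections 3.3 and 10.6 are redacted and cannot be checked.

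**Effect per patient.** Let d be the number of patients with pre-existing KS. Each omitted case lowers the rate by 100/d percentage points. The only document input is the planned enrolment of 27 (section 10.2), so d is at most 27 and the shift is at least 100/27 = 3.7 points. The documents give no share with pre-existing KS. Assuming 20-50%:

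- 20% of 27 is about d = 5, so 100/5 = 20 points per case.
- 50% of 27 is about d = 14, so 100/14 = 7.1 points per case.

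**Illustration (assumed: d = 10, with 4 patients meeting 3.2.7; exact 95% intervals)**

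| Of the 4, number needing treatment | 3.2.7 rate | 10.5.4 rate |
|---|---|---|
| 4 | 40% (12-74) | 40% (12-74) |
| 2 | 40% (12-74) | 20% (3-56) |
| 0 | 40% (12-74) | 0% (0-31) |

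The intervals are wide and overlap. What is at issue is which quantity is reported; a trial of this size could not show a difference between the two.

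**Comparability.** The background figures are described as KS exacerbation (36-75%, section 1.3) and KS progression (9/24 = 37.5%, given as 38% in section 1.4). Neither is described as need for treatment. The documents do not give those studies' detailed criteria, so the supportable statement is that comparability with the 10.5.4 rate is unclear.

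**The case against.** **The treatment threshold may be deliberate.** Need for treatment is less subjective than clinical worsening in an unblinded single-arm trial. The plan makes a similar move for relapse: 3.2.3 refers to active disease, while 7.1.6 and 10.5.2 add the need to restart treatment. This is a fair case for reporting a treatment-based rate. It does not settle the mismatch. For relapse, 7.1.6 and 10.5.2 write the condition into the definition itself. For KS, the definition appears three times without it, once directly above the estimator.

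**Untreated flares may appear as adverse events.** Section 9.1.1 defines adverse events broadly. Its exception for disease progression may refer to Castleman disease rather than KS. An early untreated flare therefore need not go unreported. The adverse event summaries still do not give a 3.2.7 rate on the pre-existing-KS denominator.

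**A reader might infer that the confidence interval is invalid**, because KS cases could include treated KS in patients outside the denominator. The documents do not support this. The sentence as a whole describes a rate of exacerbation among patients with pre-existing KS, and the natural reading keeps the numerator inside that group. At most this is a drafting ambiguity, which the fix also removes.

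**Conclusion.** The mismatch stands on the text alone: the 10.5.4 estimator is narrower than the endpoint in 2.2.7, 3.2.7 and its own heading, and no readable section reconciles them. The reported rate can understate exacerbation as defined, by at least 3.7 percentage points for each untreated exacerbation. That bound rests only on d being at most 27. The larger shifts and the illustration rest on assumed KS shares and event counts.

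Three stronger conclusions might be inferred and are not supported:

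- That the rate is certain to understate, or by a known amount. The number of untreated exacerbations is unknown and could be zero.
- That the trial plans no other KS rate of any kind. This can be said only of the readable text.
- That the trial's safety conclusion is undermined. The endpoint is secondary and descriptive, and the primary test of Grade 3 or higher non-hematologic events does not use it.

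**What to change.** In 10.5.4:

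1. Make the numerator the number of patients with pre-existing KS who have at least one exacerbation meeting 3.2.7. Keep the denominator and the 95% interval.
2. Report the subset requiring KS-specific treatment as a second rate on the same denominator.
3. State one follow-up window for both rates.
4. List 3.2.7 events in patients without pre-existing KS separately, outside both rates.

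The cost is two or three sentences. History and physical examination are already scheduled at every visit in Table 7, so no visit or sample is added. If the window runs past week 5, the case report form should capture the start of KS treatment, because Table 7 appears to schedule concomitant medications only to the end-of-treatment visit.

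The drawback is that the broader count relies more on clinical judgement. Keeping the treatment-based rate beside it answers that, and nothing now planned is lost.

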3.2.9 Hemoglobin (grams per deciliter (g/dL)), platelet count (microliters (μ l)), and C-reactive protein (CRP; milligrams per milliliter (mg/mL)) will be measured at baseline, day 15, and end-of-treatment.

3.2.10 Change in Kaposi sarcoma herpesvirus viral load will be measured in copies per milliliter at baseline, day 15, and end of treatment.

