10.2 Sample Size, Accrual and Duration of Accrual

To assess safety, toxicities will be monitored, graded, and documented by investigators at each clinic visit. Rituximab-based treatment will be considered safe in this population provided <40% non-hematologic AEs; we hypothesize that the true rate will be around 20%, based on previous studies.^{9,10,15,16} With a sample size of 24 patients, we reach 80% power to reject (if we observe $\leq 6 \geq$ Grade 3 AEs) the null hypothesis (H_0 : toxicity rate $>40\%$) using a one-sided exact test at $\alpha=0.1$. To account for 10% possible loss to follow-up during the toxicity-monitoring period, we will plan to enroll 27 patients. We plan to enroll approximately 10 patients annually and therefore expect to accrue patients for a total of three years.

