The MCD symptom score will be summed and differences across treatment will be compared using a paired t-test. We hypothesize that quality of life will be significantly improved from baseline to end of treatment with rituximab-based treatment (the MCD symptom score will be lower and PRO-Pr will be higher in utility).

10.5.6 To describe the trends in hemoglobin, platelet count, CRP, IL-6, IL-10, and KSHV viral load before, during, and after treatment with a risk-adjusted, rituximab-based treatment for MCD in Malawi, and to describe the utility of these markers as a predictor of relapse.

Hemoglobin, platelet count, CRP, IL-6, IL-10, and KSHV viral load will be measured at baseline, day 15, and end-of-treatment. Differences will be compared by paired t-test. We hypothesize that hemoglobin, platelet count, CRP, and plasma KSHV viral load will be strongly associated with disease activity (hemoglobin and platelet count will increase in remission and CRP and KSHV viral load will decrease in remission).

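### Section 10.5.6 sets no analysis scale and no rule for undetectable values for KSHV viral load, CRP, IL-6 and IL-10; if they are strongly skewed, a raw-scale paired t-test could miss a real fall, mainly in viral load

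*Combined protocol and SAP*

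**What the plan says.** Section 10.5.6 lists the markers and time points: "Hemoglobin, platelet count, CRP, IL-6, IL-10, and KSHV viral load will be measured at baseline, day 15, and end-of-treatment". The whole analysis method is then "Differences will be compared by paired t-test". The same section states the expectation that "CRP and KSHV viral load will decrease in remission"; it gives no direction for IL-6 or IL-10.

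The scale appears only in the endpoint definitions. Section 3.2.10 has "Change in Kaposi sarcoma herpesvirus viral load will be measured in copies per milliliter at baseline, day 15, and end of treatment", and section 3.2.9 has "C-reactive protein (CRP; milligrams per milliliter (mg/mL)) will be measured at baseline, day 15, and end-of-treatment".

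The readable text gives no transformation, rank-based alternative, distribution check or treatment of values below the assay limit. It also gives no mean, SD or expected change for any marker. The only power statement, in section 10.2, concerns the primary safety endpoint.

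**The concern.** A paired t-test on natural units compares the mean absolute difference with its standard error. When values are strongly right-skewed, a few patients with high baselines supply most of the mean difference and most of its variance. The test can then be non-significant although nearly every patient's value fell.

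Secondary objectives 2.2.9 (marker trends) and 2.2.11 (viral load change) rest on this comparison. The trial has one arm, so within-patient change is the only evidence on them. A viral load that fell consistently could be reported as showing no significant change.

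Two further problems follow from the missing detail. If the scale is left open, it can be chosen after the data are seen. And if treatment lowers viral load as hypothesised, some follow-up values may be undetectable, for which no rule exists.

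**Working it through.** **Number of pairs.** Section 10.2 states "With a sample size of 24 patients, we reach 80% power to reject" when 6 or fewer events are seen, with a null rate of 40%, an expected rate of 20% and one-sided alpha 0.1. Exact binomial: P(X ≤ 6 | 24, 0.40) = 0.096 and P(X ≤ 6 | 24, 0.20) = 0.811. Inflation: 24 / 0.9 = 26.7, so 27. The design figures reproduce, and 24 pairs is a fair basis. There is no stated figure for the marker tests to reproduce.

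**Assumptions not in the documents.** Values are log-normal with the same log10 SD (s) before and after treatment. Within-patient correlation on the log scale is ρ = 0.5, and the test is two-sided at 0.05. The SD of the log10 change is s√(2(1 − ρ)), which equals s when ρ = 0.5.

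**Log10 power.** This follows from the noncentral t with 23 df and noncentrality (log10 fall / SD of change) × √24. For a 10-fold fall at s = 1.0 it is 1 × 4.90 = 4.90, giving power above 99%. At s = 1.25 it is 4.90 / 1.25 = 3.92, giving 96%.

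**Raw-scale power.** This was simulated. The last column is the median share of the baseline total held by the single highest of 24 patients.

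| log10 SD | 10-fold fall, raw | 10-fold fall, log10 | 3-fold fall, raw | 3-fold fall, log10 | Highest patient's share |
|---|---|---|---|---|---|
| 0.5 | 97% | 100% | 82% | 99% | 21% |
| 0.75 | 69% | 100% | 31% | 84% | 32% |
| 1.0 | 34% | >99% | 10% | 61% | 43% |
| 1.25 | about 15% | 96% | 4% | 44% | 52% |

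**Sensitivity.** At s = 1.0, moving ρ from 0 to 0.8 moves raw power for a 10-fold fall from 27% to 45%; log10 power stays at 91% or more. With 20 pairs at s = 1.0 and ρ = 0.5 it is 29% against 99%. The Wilcoxon signed-rank test with 24 pairs gives 97% at s = 1.0 and 86% at s = 1.25.

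**A check without variability of response.** Suppose every patient's value falls by exactly the same factor k. The raw difference is then −(1 − 1/k) times baseline, the factor cancels, and |t| = √24 / CV, where CV is the sample coefficient of variation at baseline. Significance needs CV below 4.90 / 2.07 = 2.37, whatever the size of the fall. By simulation this happens in 78% of trials at s = 0.75, 52% at 1.0 and 32% at 1.25. So a perfectly uniform fall can be missed on the raw scale.

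**Modest spread, as CRP might have.** Take s = 0.3 to 0.4, SD of change 0.4 log10 and a 2-fold fall (0.30 log10). Equal spread implies ρ = 1 − 0.4² / (2s²), which is 0.11 at s = 0.3 and 0.50 at s = 0.4. Raw power is about 87% and 77% respectively. Log10 power is 94% in both cases (noncentrality 0.30 / 0.4 × 4.90 = 3.7).

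**The case against.** The plan never says that values will be analysed untransformed. Copies/mL and mg/mL are units of measurement, and a paired t-test on log10 values would comply with section 10.5.6. That is right: a reader might infer that the plan requires a raw-scale test, but the text is silent. The silence still matters, because the natural reading of a t-test on endpoints given in these units is the raw scale, and nothing fixes the choice in advance.

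A reader might also infer that the raw test would probably miss a real fall in all four markers, or that a few high values are bound to dominate. The documents do not support this, because they give no distribution for any marker. At log10 SD 0.5 or below, the raw test detects a 10-fold fall with at least 96% power. Power for that fall drops below 50% only when the SD is near 1.

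Much worse figures for CRP, around 38% to 40%, can be produced by adding a random change that is independent of baseline. That model makes values more spread out after treatment than before, and nothing in the documents suggests it. Pushed further, it defeats its own purpose. With a change SD of 1.0 log10, a median 10-fold fall goes with a rise in the arithmetic mean of 0.1 × exp((ln 10)² / 2) = 1.42-fold, so the raw test is then faulted for not finding a fall in a mean that rose.

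Finally, these objectives are secondary and largely descriptive, with no success criterion or power claim, and the stated hypothesis concerns disease activity in remission rather than a significant change in all patients. This limits the consequence but does not remove the reason to specify the method.

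**Conclusion.** The point holds as a conditional one. The plan names a paired t-test for markers that may be strongly skewed and fixes neither the scale nor the handling of undetectable values. If the log10 SD is about 0.75 or more, a raw-scale analysis with 24 pairs loses much of its power: 31 percentage points for a 10-fold fall at 0.75 (100 − 69) and about 65 at 1.0. Viral load is the likeliest marker to be affected. For a marker with log10 SD 0.3 to 0.4 the loss is about 7 to 17 points (94 − 87 and 94 − 77).

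These sizes rest on log-normality, equal spread before and after treatment, the stated correlations and a two-sided 5% test, none of which the documents give. In the log-normal, equal-spread scenarios examined, the raw test never had more power than the log10 test. The primary safety analysis does not use these tests and is unaffected.

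**What to change.** In section 10.5.6:

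- Analyse KSHV viral load, CRP, IL-6 and IL-10 as paired differences on the log10 scale, and report geometric mean ratios to baseline with 95% CIs.
- State in advance how values below the detection limit enter the analysis, and name the proportion of undetectable values above which the Wilcoxon signed-rank test replaces the t-test.
- Keep the natural scale for hemoglobin and platelet count.

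This changes analysis wording only and needs no extra patients, samples or visits. The price is that results for the four markers are reported as fold changes rather than absolute changes. If absolute changes are also wanted for clinical reading, medians and ranges can be shown descriptively.
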